2.2. Supporting Pilot / Unpublished Data

Prebiotics significantly affect gut health and microbiota composition. The impact of recognized prebiotics, or functional foods that stimulate growth of gut native beneficial bacteria, on microbiome composition and functionality has been documented by us and others^{3, 4, 11}. β (1-4) galacto-oligosaccharides (**GOS**) are complex carbohydrates that resist digestion in the upper GI tract, and thus arrive to the colon intact and consequently increase the abundance of specific primary and secondary metabolizers. Studies have reported the beneficial impact of GOS, alone or in combination with probiotics, on bowel function^{12, 13}, diarrhea and abdominal pain^{10, 11, 14, 15}, bloating and flatulence^{16, 17} in adult individuals. N-Acetyl-D-lactosamine (**LacNAc**, Gal β 1,4GlcNAc) is a biologically relevant molecule that is a building block of gut glycoproteins, and a precursor of several important blood group epitopes, including Lewis A, Lewis B, or sialyl Lewis A, which are involved in biological processes, including fertilization and pathogen recognition¹⁸. Of relevance for our study, repeating and variably branched lactose or LacNAc units, frequently with attached sialic acid and fucose monosaccharides, compose complex human milk oligosaccharides (HMOs), which are uniquely abundant in human breast milk but not in that of other mammals¹⁹⁻²¹. Most HMOs are not digested by human enzymes, acting as natural prebiotics for the development of a healthy gut microbiota in infancy^{7, 8, 22}. While GOS is not a naturally occurring non-digestible carbohydrate, it does share structural similarities with LacNAc, with the latter containing nitrogen molecules attached to the disaccharide backbone. Despite the biological relevance of LacNAc, no studies have addressed its impact on human gut physiology and the microbiota since the chemical methods to generate LacNAc demand multi-step syntheses and are expensive and labor intensive. Likewise, current enzymatic methods use galactosyl-transferases, which require UDP-galactose as a glycosyl donor²³, and have high acceptor selectivity, yielding low efficiency with unnatural acceptors²⁴.

GOS and hGOS beneficially impact the gut microbiome, increasing beneficial bacteria (*Bifidobacterium* and *Akkermansia*) and saccharolytic potential of the microbiota and reduced intestinal permeability, modulating markers of inflammation⁹. Furthermore, GOS, but not hGOS, increased mucus in the intestinal lumen, suggesting different mechanisms of action. Our previous studies in mice have shown that short-term feeding of pure GOS increases expression of protective mucus-producing *MUC2*, decreases intestinal permeability, and reverses proportions of fecal β -galactosidases and β -glucosidases, reflecting increases in saccharolytic bacteria, including *Bifidobacterium*^{9, 25}.

In this trial, we will determine changes in the abundance of saccharolytic bacteria as described⁹. Briefly, we will use a reference study that mined 532 publicly available gut reference genomes and assigned them to four different groups (proteolytic, saccharolytic, lipolytic, and generalist bacteria) using metagenome analytical methods²⁶, and the metabolic reconstruction network AGORA²⁷. In the case that the genus is not categorized in the mentioned studies, will refer to the Bergey's Manual of Systematic Bacteriology and previously published reports.

2.3. Scientific Rationale

The study will test two prebiotics: highly pure GOS and LacNAc-enriched GOS (hGOS). The intervention will include a dose of 15 g daily as previously reported¹⁰. Dose was selected based on previous literature reports^{16, 17, 28-30} and the interventions conducted by our group to assess efficacy of GOS in lactose-intolerant individuals^{10, 11, 31, 32}. The hGOS targeted dose will be composed of 15g of GOS enriched with 150 mg of LacNac (99:1), which is in agreement with the range found in human breast milk³³. Based on the concentration detected in breast milk, an infant consumes between 54 and 243 mg of LacNAc per day, with the variation depending on stage of lactation and infant age and weight.

Participants will be assigned randomly to one of 3 groups (n = 16): GOS, hGOS or placebo (powdered corn syrup comprised of fructose, glucose, and an inert cellulose material that matched the consistency, color, sweetness, and taste of the prebiotics)^{10, 32} to test safety and dose tolerability. The prebiotic treatment will last for 4 weeks, since we have shown in adult individuals that a 4-week period allows for the observation of changes to the gut microbiome^{10, 11}. The doses of GOS, hGOS and placebo will be increased over 28 days beginning with 10 g/day and increasing to 15 g/day. Dose regimen will be 5 grams twice daily on days 1–10 followed by 7.5 grams twice daily on days 11–28. Doses will be in powder form and will be mixed with water or food and taken as directed by the dosing scheme.

High-sensitivity C-reactive protein (hs-CRP) is a recognized marker of systemic inflammation³⁴ and specific pro-inflammatory cytokines mediate interaction between immune cells and non-immune cells, contributing to the inflammatory status of the intestine^{35, 36}. Based on previous studies with probiotics and prebiotics that report potential immunomodulatory effects³⁷⁻³⁹, we decided to monitor hs-CRP, IL-1 α , IL-1 β , IL-2, IL-6, IL-8, IL-12, TNF α , and IFNy for the duration of the clinical trial.

Before the treatment (baseline) and during week 4 of the trial (after the prebiotic treatment), we will assess changes in quality and quantity in bacterial components of the gut microbiome pre- and post-treatment. Likewise, we will determine serum inflammatory markers, and integrity of the intestinal barrier at baseline and at week 4. Subjects will also respond to the Diet History Questionnaire (DHQ), a freely available food frequency questionnaire (FFQ) and will be asked to keep daily diet records.

3. Objectives

3.1. Specific Aim 1

To validate 15 g/day dose safety and tolerability of GOS and hGOS in **healthy adults**.

3.2. Specific Aim 2

To establish a biological signature of GOS and hGOS through assessment of prebiotics effects vs placebo on (i) abundance of beneficial gut bacteria and restoration of the gut microbiome saccharolytic potential, (ii) modulation of biomarkers of inflammation and (iii) evaluation of intestinal barrier function.

4. Study Design

[figure not shown]
This will be a controlled (GOS, hGOS versus placebo), interventional, longitudinal (baseline compared to end of study), prospective, single-site pilot study. Subjects will be assigned randomly to one of 3 groups (n = 16): GOS, hGOS or placebo. The treatment will consist in 10 - 15 g/day of GOS, hGOS or placebo (powdered corn syrup comprised of fructose, glucose, and an inert cellulose material that matched the consistency, color, sweetness, and taste of the prebiotics), which will be provided to participants as powder that can be added to any non-alcoholic beverage or sprinkled on food for intake. The intervention will last for 4 weeks, since we have shown in adult individuals that a 4 week period allows for the observation of changes to the gut microbiome. The study will end after the second time-point sample collection at 4 weeks.

Dose rationale: The intervention will include a dose of 5 grams twice daily on days 1–10 followed by 7.5 grams twice daily on days 11–28¹⁰. Doses were selected based on previous literature reports^{16, 17, 28-30} and the interventions conducted by our group to assess efficacy of GOS in lactose-intolerant individuals^{10, 11, 31, 32}. The hGOS preparation will be composed of GOS enriched with LacNac at a concentration of 6.7–31µg/mL (<1% of the formulation), which is in the range found in human breast milk³³ and hence considered safe.

Flow diagram

Prior to Enrollment

Obtain informed consent. Screen potential participants by inclusion and exclusion criteria; obtain medical history, document. **Total N = 48**

Visit 1

Time Point

Weekly GSSC data collection

Visit 2
Time Point

4 weeks: collect blood and stool. Administer 38-point Gastrointestinal Symptom and Severity Checklist (GSSC) Questionnaire (FFQ)

Analyses: (a) Evaluation of inflammation and intestinal barrier function in serum; (b)

4.1.Treatment Design

Dose rationale. The intervention will include a dose ranging between 10 to 15 g daily as previously reported¹⁰. Doses were selected based on previous literature reports^{16, 17, 28-30} and the interventions conducted by our group to assess efficacy of GOS in lactose-intolerant individuals^{10, 11, 31, 32}. The hGOS preparation will be composed of GOS enriched with LacNac at a concentration of 6.7-31 μ g/mL (<1% of the formulation), which is in the range found in human breast milk³³ and hence considered safe.

Regimen. The prebiotics dose will be 5 grams twice daily on days 1–10 followed by 7.5 grams twice daily on days 11–28. The placebo (powdered corn syrup comprised of fructose, glucose, and an inert cellulose material that matched the consistency, color, sweetness, and taste of the prebiotics) will be administered in a blinded matching packet at the same doses. If participants miss taking a dose on a given day, they will be directed to put the pouch for that day aside, and on the next day take the next numbered pouch.

4.2.Experimental / Observational Design

Subjects will be assigned randomly to one of 3 groups (n = 16): GOS, hGOS or placebo.

4.3.Measurement Design

Blood and stool samples will be collected at baseline (Day 0) and end of treatment (Day 28). Stool collection kits will be provided to participants in case samples cannot be obtained *during study visits*. Safety and tolerability will be determined based on the severity and/or frequency of side effect using a 38-point Gastrointestinal Symptom and Severity Checklist (GSSC). In addition, tolerability will be evaluated through occurrence of drop-out and adherence.

Measurements on blood (10 mL per visit for a total of 20 mL):

- (1) Fasting venous blood samples will be drawn and serum will be used to quantify zonulin using the Zonulin (IDK® Zonulin) (Serum) ELISA test (Immundiagnostik AG).
- (2) Determination of levels of biomarkers of inflammation (IL-1 α , IL-1 β , IL-2, IL-6, IL-8, IL-12, TNF α , and IFNy) as well as high-sensitivity C-reactive protein, a marker of low-grade inflammation (hsCRP) in serum. We will determine cytokine levels using the MCYTOMAG-70K (Milliplex) in the Advanced Analytics Core (AAC) of the CGIBD. (ii) hsCRP concentration will be measured via hsCRP ELISA (Sigma Aldrich).

Measurements in stool:

Determination of abundance of beneficial bacteria (*Bifidobacterium* and *Akkermansia* species) in the gut microbiome of treatment and placebo groups and the microbiome saccharolytic potential using WGS sequencing, the most accessible, cost-effective measure currently available.

4.4.Outcome Measures

Primary Outcome(s):

The expected outcome is to confirm a 15 g/day as a safe and tolerable dose of GOS and hGOS in healthy adult individuals using the 38-point Gastrointestinal Symptom and Severity Checklist (GSSC).

Secondary Outcome(s):

Definition of prebiotic biosignature characterized by:

- Increased abundance of saccharolytic bacteria (*Bifidobacterium*) and other beneficial bacteria (*Akkermansia*)
- Modulation of biomarkers of inflammation
- Improved intestinal barrier function.

Tertiary/Exploratory Outcome(s): N/A

Other Measures: Baseline Characteristics and Assigned Treatments: N/A

5. Study Participants

5.1. Number of Participants

Number to be recruited for screening: 55-60 participants will be recruited for screening.

Number of eligible participants enrolled: The targeted number of participants is 48. We expect that 20% of screened individuals will not be eligible or will be unwilling/unable to participate in the study. Participants will be adults (male and female, 18-55 years old with no formal diagnosis of IBD, IBS, UC, CRC, celiac disease, or diabetes mellitus) recruited at UNC Chapel Hill and within the general population in the surrounding area via email communications, social media, and flyers.

Subjects will not be diagnosed with specific GI conditions (IBD, IBS, UC, CRC) and with no history of celiac disease, diabetes mellitus or antibiotic consumption in the previous 2 months. Individuals with a non-GI related disease diagnosis might be included in the study.

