Target Population	
Healthy adult individuals
 
Key Inclusion Criteria: Individuals ages 18-55 with BMI of 18.5 to 32.
 
Key Exclusion Criteria:
 
 Formal diagnosis of IBD (including ulcerative colitis, Crohn's Disease) colorectal cancer, diabetes Celiac disease or IBS diagnosed by a physician Lactose intolerance as diagnosed by a hydrogen breath test C. difficile infection within 2 months Antibiotic consumption in the previous 2 months History of gastric bypass surgery Current tobacco smoker Pregnant or breastfeeding A response of 4 or 5 to questions 2 (abdominal pain), 6 (abdominal discomfort), 8 (constipation), 16 (diarrhea), 22 (abdominal distention), 26 (abdominal bloating), 31 (nausea), or 33 (vomiting).
Numbers of Participants	
Number to be recruited for screening: 55-60 participants
 
Number of eligible participants enrolled: 48 adult individuals

Clinical Phase	Pilot
Intervention	Daily oral administration of 10 - 15 g of Prebiotic galacto-oligosaccharides (GOS) or GOS enriched with lactosamine (LacNAc) for four weeks
Study Description	We will enroll 48 adult individuals (18-55 y.o.). Subjects will be assigned randomly to one of 3 groups (n = 16): GOS, hGOS or placebo (powdered corn syrup comprised of fructose, glucose, and an inert cellulose material that matched the consistency, color, sweetness, and taste of the prebiotics) to test safety and dose tolerability. The prebiotic treatment will last for 4 wk. Before the treatment (baseline) and during week 4 of the trial (after the prebiotic treatments), we will assess changes in quality and quantity in bacterial components of the gut microbiome pre- and post-treatment. Likewise, we will

	determine serum markers of inflammation, integrity of the intestinal barrier at baseline and at week 4. Participants will complete the Diet History Questionnaire (DHQ), a freely available food frequency questionnaire (FFQ) at baseline and will be asked to maintain a record of their daily diet by using a printed meal tracking diary. In addition, the PROMIS Gastrointestinal Symptom Scale will be used for potential side effect evaluation at baseline and each week for the duration of the study.
Outcome Measures	Dose safety and tolerability in healthy adults . Gut microbiome Inflammation Integrity of intestinal barrier
Study Duration	4 weeks
Subject Participation Duration	4-5 weeks
Estimated Time to Complete Enrollment	40 weeks

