5.2. Eligibility

Eligibility criteria are based on self-reported information from study participants.

Inclusion Criteria:

- Individuals must be between 18 and 55 years old.
- All participants will not be tobacco smokers and will be well-nourished according to standard anthropometric criteria with BMI between 18.5 and 32.
- Individuals must be able to give informed consent.
- Subjects willing and able to:
 - consume prebiotics or placebo preparations for a period of 4 weeks
 - record daily food consumption using hard-copy food diary provide at the baseline visit, and complete the Diet History Questionnaire (DHQ).
 - provide stool, and blood (via venipuncture) samples.
- Enrollment will not be restricted based on race, ethnicity, or gender. Subject population will reflect the population providing a broad selection of individuals to allow to enroll subjects from all races, ethnicities and genders as represented in North Carolina state.

Exclusion Criteria:

- Individuals diagnosed with Inflammatory Bowel Diseases (IBD), Ulcerative Colitis (UC), Colorectal Cancer (CRC) , or diabetes mellitus.
- Celiac disease or IBS diagnosed by a physician

- Lactose intolerance as diagnosed by a hydrogen breath test
- C. difficile infection or treatment within 2 months
- Individuals currently or within the past 2 months on prescribed antibiotics.
- Patients with a history of gastric bypass surgery.
- Any physical or psychological condition that, in the opinion of the investigators, would pose unacceptable risk to the patient or raise concern that the patient would not comply with protocol procedures
- Women that are pregnant or breastfeeding will be excluded from the study.
- A response of 4 or 5 to questions 2 (abdominal pain), 6 (abdominal discomfort), 8 (constipation), 16 (diarrhea), 22 (abdominal distention), 26 (abdominal bloating), 31 (nausea), or 33 (vomiting) on the PROMIS Gastrointestinal Symptom Scale.

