8.5. Baseline Characteristics of the Participants

Apparently healthy adults 18-55 years old. All participants will be nonsmoking and well-nourished according to standard anthropometric criteria.

Enrollment will not be restricted based on race, ethnicity, or gender. Subject population will reflect the population in the long-term care facility providing a broad selection of individuals to allow to enroll subjects from all races, ethnicities and genders as represented in North Carolina state.

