Rationale. High-sensitivity C-reactive protein (hs-CRP) is a recognized marker of systemic inflammation³⁴ and specific pro-inflammatory cytokines mediate interaction between immune cells and non-immune cells, contributing to the inflammatory status of the intestine^{35, 36}. Based on previous studies with probiotics and prebiotics that report potential immunomodulatory effects³⁷⁻³⁹, we decided to monitor hs-CRP, IL-1 α , IL-1 β , IL-2, IL-6, IL-8, IL-12, TNF α , and IFN γ for the duration of the clinical trial.

Method. Determination of levels of biomarkers of inflammation (IL-1 α , IL-1 β , IL-2, IL-6, IL-8, IL-12, TNF α , and IFN γ) as well as high-sensitivity C-reactive protein, a marker of low-grade inflammation (hsCRP) in serum. We will determine cytokine levels using the MCYTOMAG-70K (Milliplex) in the Advanced Analytics Core (AAC) of the CGIBD. hsCRP concentration will be measured via hsCRP ELISA (Sigma Aldrich).

Statistical analysis (A2.2). Similar to A2.1, we will perform an exploratory analysis of changes in plasma cytokines. Data will be presented as mean \pm SD. To find the change of biomarker of interest under difference circumstance, paired t-test for matched pair between baseline and 4 weeks follow-up will be performed for levels of biomarkers in each treatment arm. To compare the change of biomarker level in three arms, we will use ANOVA to test whether the change of biomarker level is the same among three groups. Due to multiple testing, p values will be corrected for the total number of comparisons with a controlled false-discovery rate (FDR)

(A2.3) Evaluation of intestinal barrier function.

Method. Blood samples will be drawn and serum will be used to quantify zonulin using the Zonulin (IDK® Zonulin) (Serum) ELISA test (Immundiagnostik AG). Zonulin is a biomarker of impaired intestinal permeability, which has been associated with various disorders^{56, 57}.

Statistical analysis (A2.3). Since A2.3 has similar data and analytic goal as A2.2, the analytic approach will be the same as what we proposed in A2.2.

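### No rule links acute illness or anti-inflammatory drug use to the two blood draws behind A2.2 and A2.3, so one ill draw can dominate an arm's mean change

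*Combined protocol and SAP*

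**What the plan says.** **Population.** Section 8.5 describes "Apparently healthy adults 18-55 years old", while section 5.1 adds: "Individuals with a non-GI related disease diagnosis might be included in the study". Section 5.2 excludes a list that ends "Ulcerative Colitis (UC), Colorectal Cancer (CRC) , or diabetes mellitus". It also bars smokers, BMI above 32, pregnancy, several GI conditions and "Individuals currently or within the past 2 months on prescribed antibiotics". A discretionary clause covers "Any physical or psychological condition that, in the opinion of the investigators, would pose unacceptable risk to the patient" and doubts about compliance, but not the validity of a marker. The source is stated plainly: "Eligibility criteria are based on self-reported information from study participants".

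**Measurement.** Section 4.3 takes blood at Day 0 and Day 28. Section 7.6 gives the final visit a window of ±2 days. The only stated condition on a draw is fasting.

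**Records of illness and drugs.**
- Section 6.4 requires new diagnoses and new therapies to be disclosed and discontinues anyone given antibiotics on study.
- The table of events in 7.1 collects medical history and concomitant medications at screening and at the final visit.
- Section 10.3 puts an open question about health changes at each visit, and files changes between consent and first dose as medical history.
- Section 10.4 assesses participants on days 0, 7, 14, 21 and 28.
- The Visit 1 list in 7.4 has no illness or medication item.

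**Analysis.** For A2.2, a "paired t-test for matched pair between baseline and 4 weeks follow-up will be performed for levels of biomarkers in each treatment arm", with ANOVA on change between arms. A2.3 follows the same approach. The synopsis alone offers median (IQR) and Kruskal-Wallis for non-normal data. Section 6.2 unblinds the team after samples are processed and before analysis.

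**Status.** Section 4.4 lists inflammation and barrier function as secondary outcomes. A2.2 and section 9.5 call the biomarker analysis exploratory, without expected power.

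**The concern.** Each participant's change is one value minus another. hs-CRP and several of the cytokines respond to infection, injury, vaccination and anti-inflammatory drugs on a scale that can far exceed any plausible prebiotic effect. If the Day 28 draw falls during such an episode, the arm appears to worsen. If the Day 0 draw does, recovery looks like an anti-inflammatory effect. With about 16 people per arm, a statistic built on the mean has little protection.

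The plan gathers much of the information needed to recognise such a sample but never says what to do with it. No provision postpones, repeats, flags or sets aside a draw. Because the team knows the arms before it analyses, an exclusion decided at that stage could not be defended as blind. What is at stake is whether the A2.2 and A2.3 summaries, which section 9.5 falls back on comparing as means and standard errors, describe the arm or one person in it.

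**Working it through.** **1. Arm size.** Section 9.5: 60 × (1 − 0.20) = 48, and 48 / 3 = 16. This reproduces. The biomarker paragraph of 9.5 mentions n=20 and section 8.6 mentions 45 randomised; 16 is used here. No SD, effect size, alpha or illness rate is given for the biomarkers, so those below are assumptions.

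**2. One ill draw at Day 28, no true effect.** Assume 15 people have hs-CRP changes with mean 0 and SD 1 mg/L, and one has a change of X.
- Mean = X / 16
- SD = √[(14 × 1² + (15/16) × X²) / 15]
- X = 20: mean 1.25; SD = √(389 / 15) = 5.09
- X = 50: mean 3.125; SD = √(2357.75 / 15) = 12.54

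The 95% half-width is 2.131 × SD / √16 (t with 15 df). It is about 0.53 for a clean arm with SD 1, 2.71 at X = 20 and 6.68 at X = 50. If the ill draw is at Day 0, the mean has the opposite sign and the SD is the same. With 13 completers the shifts are 20/13 = 1.54 and 50/13 = 3.85.

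**3. Can it create significance?** t = (X/16) / (SD/4). This is 0.98 at X = 20 and 1.00 at X = 50, and its limit is 1, well short of 2.131. Simulation of three arms of 16 with no effect agrees: ANOVA rejects in 5.1% of runs with clean data, 1.7% with one 10 SD outlier and about 0% with one 20 SD outlier.

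**4. Can it hide or distort a real effect?** Assume a true change of −1 SD in the arm. The mean is −1 + X/16 and the SD is as in step 2. Clean: t = −1 / 0.25 = −4.0.

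| X (in SD) | Mean | SD | t |
|---|---|---|---|
| +5 | −0.69 | 1.58 | −1.74 |
| +10 | −0.38 | 2.68 | −0.56 |
| +20 | +0.25 | 5.09 | +0.20 |
| −5 | −1.31 | 1.58 | −3.32 |
| −10 | −1.63 | 2.68 | −2.43 |
| −20 | −2.25 | 5.09 | −1.77 |

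An outlier against the effect hides it and can reverse its sign. One in the same direction exaggerates the mean while widening the SD.

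Simulated power for the opposing case (two-sided 0.05, 16 per arm):

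| Test | Clean | 5 SD | 10 SD | 20 SD |
|---|---|---|---|---|
| ANOVA | 81% | 26% | 0.3% | ≈0% |
| Paired t | 96% | 29% | ≈0% | ≈0% |
| Kruskal-Wallis | 78% | 58% | 57% | 57% |
| Wilcoxon | 94% | 70% | 69% | 68% |

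**5. How often might a draw be affected?** An arm has 16 × 2 = 32 draws. P(at least one) = 1 − (1 − p)^32. For p = 1%, 2%, 3%, 5% this is 28%, 48%, 62%, 81%. These rates count any acute illness. How many would produce a 20 to 50 mg/L rise is unknown, so steps 2 and 5 should not be multiplied together.

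**The case against.** The strongest reply has four parts.

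*The plan already checks for illness.* Largely true. Health changes are asked about at each visit, days 0 and 28 are assessment days, and medications are collected again at the final visit. Antibiotic-treated participants are discontinued (6.4), and section 7.8 then leaves them out of Objective 2. A reader might infer that the plan ignores illness; the documents do not support that. The gap is that no rule uses the records at the draw or in the analysis. It is widest at Day 0, where the visit list has no such item and screening may be 14 days earlier.

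*The admission of non-GI disease is not the driver.* This stands. A reader might infer that any disease and its drugs are let in, and that eligibility must be tightened. Diabetes, recent antibiotics and conditions judged an unacceptable risk are barred. Stable disease largely cancels in within-person change, and healthy people fall ill too. No calculation here shows harm from the 5.1 sentence itself, and narrowing entry would also narrow the population for the primary tolerability aim.

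*Randomisation protects the comparison.* In expectation, yes. The synopsis entry "Estimated Time to Complete Enrollment" is 40 weeks, but season and infection should affect all arms alike. A reader might fear a false anti-inflammatory finding; step 3 shows that a single extreme value does not produce significance, and section 9 reports non-significant results as inconclusive. What remains is imprecision and a misleading arm mean.

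*The analysis is exploratory and has fallbacks.* Kruskal-Wallis appears in the synopsis but not in A2.2. The sensitivity commitment in section 9 is general and names neither illness nor outliers. Exploratory status lowers the stakes, yet the fallback of comparing means and standard errors uses exactly the statistics that one ill draw distorts.

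**Conclusion.** The point holds as a gap in measurement and analysis rules: illness and drug information is collected but never tied to the two samples on which A2.2 and A2.3 depend, and the planned tests are sensitive to one extreme change. On the assumed values, one affected draw among 16 moves the arm mean by 1.25 to 3.1 mg/L and raises the SD from about 1 to between 5.1 and 12.5. Against an assumed 1 SD effect, one opposing 5 SD outlier cuts ANOVA power from 81% to 26%; rank tests lose less.

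These sizes rest on assumed hs-CRP rises, SDs, effect and alpha; the frequency rests on an assumed illness rate per draw. Only hs-CRP is illustrated in its own units. The consequence is a noisier and possibly misleading estimate in a secondary, exploratory analysis. It does not bear on the primary tolerability aim, does not amount to systematic bias or false significance, and does not justify changing eligibility. It is worth fixing because the fix is cheap and has to be set before unblinding to be credible.

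**What to change.** 1. **Sections 7.4 and 7.6:** at both blood-draw visits, record acute illness, fever, vaccination and anti-inflammatory drug use in the preceding 7 days. Where the answer is yes, move the draw within the existing windows (up to 14 days after screening for Day 0, ±2 days for the final visit) if possible. Otherwise take the sample and flag it. Two days will often be too short at the final visit, so the flag matters more there.
2. **Section 9.2 (A2.2 and A2.3) and section 6.2:** state that flags are fixed before unblinding, and that both analyses are repeated without flagged samples and reported beside the main result.
3. **Section 9.2 and the synopsis:** reconcile them so that skewed markers are analysed by rank methods or on the log scale. Ranks bound the influence of one value. Logs shrink it without bounding it: from an assumed 1 mg/L, rises of 20 and 50 mg/L become ln 21 = 3.0 and ln 51 = 3.9.

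Leave the eligibility criteria as they are for this purpose.

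Cost: one short question at two existing visits, occasional rescheduling, slightly fewer samples in the repeat analysis, and one extra analysis run. Rank tests also give up a little power when the data are clean (78% against 81% for ANOVA in the simulation).
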